1 STUDY OBJECTIVES

1.1 Hypothesis: Immigrants in the Problem Management Plus for Immigrants (PMP-I) will have significantly lower stress and anxiety/depressive symptoms than immigrants in the talk program with Community Support Service pamphlets (CSS).

1.2 Objective: The current study aims to pilot test the feasibility and acceptability of PMP-I among Bhutanese immigrants 18 years and older living in Massachusetts.

Aim 1: Adapt and culturally modify PMP to develop PMP-I as a family-based preventative intervention.

- a) Develop a training guide and intervention curriculum;
- b) Obtain iterative feedback about the format, ease of use, and implementation barriers from participants, facilitators, and community members.

Aim 2: Test the feasibility, acceptability, and preliminary outcomes of PMP-I with trained community facilitators.

- a) Assess i) recruitment, session attendance, and retention rates and program acceptability using checklists from participants; ii) feasibility of measures for assessing inclusion/exclusion, the fidelity of intervention delivery, mediators of response, and outcomes using checklists from facilitators; and iii) barriers and facilitators of intervention using interview and focus group discussion with participants and facilitators.
- b) Test preliminary effects of PMP-I vs. talk program with community support services pamphlets (CSS) using a small randomized pilot trial (N=116 families; 58 families per intervention and control), on perceived stress, anxiety and depressive symptoms (primary), physiological stress assessed in hair cortisol (secondary), and self-efficacy and coping strategy, family wellbeing, and social networking (targets), with assessments at baseline, post-intervention, and 3-month post-intervention.
- c) Evaluate the relationships between targets and outcomes and explore mediators (e.g., coping) of intervention-outcome relation.

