Local community members with a high school level of education and no formal training or prior experience with mental health service providers will deliver the PMP-I. First, Drs. [name] and [name] will review with the PI the PMP-I Manual, fidelity checklists, and other training materials. Second, [name] will provide ten full days (80 hours) of intensive classroom training to community interventionists (CI) using the PMP Helpers' Training Guide. Classroom training includes information about stress and depression, the rationale for each of the strategies, necessary helping skills, extensive role-plays, peer observations, and group discussion related to core intervention concepts. Third, [name] will provide an additional two days of training in supervision to the same CIs so that they can play the

dual role of interventionists and supervisors as needed. Supervision involves discussing participants' progress and difficulties experienced when delivering strategies and role-playing on managing problems or practicing skills. Fourth, following classroom training, the PI will provide field training with at least two participants for five sessions. Finally, after overall training, we will conduct a formal evaluation of the interventionists' readiness to implement/supervise the PMP-I intervention such as using the manual, answering questions, and managing time, using a fidelity checklist, practice exercise, and role play, and will provide feedback as necessary.

[name] will provide 4 hours of breathing exercises and 16 hours of yoga practice to CIs and field supervisors using a Yoga Training Guide. Classroom training includes theoretical and practice exercises to guide participants in mind-body exercises for attention to breath, body sensation, emotional awareness, and mental function on different postures of yoga practices such as *Pranayama* (3 poses) and *Asana* (21 poses). Training will include practice assessment at the end to ensure that all staff was adequately trained, using a checklist, practice exercise, and role-plays. (Please find attached the mind-body exercise manual for the details)

Intervention Components

Psychoeducation: A brief educational session on stress management to increase awareness of the health benefits of reducing stress. To address the social isolation of many immigrants' in a new culture, we plan to educate on multi-cultural communication and social networking to promote their cross-cultural interaction.

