5.2 Adherence Assessment

The PMP trainers training guidelines developed by the World Health Organization provide specific tools for evaluating and monitoring the intervention that we will use to monitor fidelity of intervention delivery. These tools are PMP Quiz, PMP Helper's Supervision Form, PMP Helper Classroom-based Competency Assessment, PMP Helper In-field based Competency Assessment, PMP Trainer/Supervisor Competency Assessment, and Session-by-Session Checklists for PMP Helpers. We have adapted these tools in the context of our program contents. (Please find attached PMP-I program monitoring tools for the details)

Using these standard tools, we will evaluate session-by-session classroom and in-field based competencies of participants, community trainers, and supervisor and provide them feedback as needed using supervision forms, role-plays, group discussion, and training. After each session and program completion, the field supervisor will collect data on engagement, acceptability, and satisfaction via a brief questionnaire and qualitative interviews with community interventionists. The field supervisor will also collect data on adherence to the manual, percent of intervention content administered, proper use of time and materials, and adequate response to participants' questions through field observation of community interventionists' work.

Field supervisors will collect data on eligibility, recruitment and enrollment, intervention session attendance (including reasons for missed sessions), and compliance with data collection procedures, including hair sample collection and anthropometric measurements using a checklist. They will monitor intervention sessions using WHO standard checklists. Items include adherence to the manual, percent of intervention content administered, proper use of time/materials, and adequate response to participants' questions. They will also collect data on engagement, acceptability, and satisfaction via

brief questionnaires and focus group discussions (FGD) with participants and interventionists after each session and upon intervention completion.

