developed in consultation with NIMH. The report will include the key variables necessary for monitoring the safety and quality of data collection and the integrity of the study, including inclusion criteria, informed consent, subject enrollment and retention, data confidentiality, intervention compliance, dropouts, adverse events, protocol compliance, data quality, and baseline characteristics of study participants. The ISM will have access to all safety and data quality information collected and have the authority to stop the study if it is determined that there are unacceptable risks to participants. The ISM will also review the study protocol, informed consent, and all relevant documents before the study's onset and review and approve amendments to these documents. The ISM will issue a monitoring report to the PI following each review. The PI will submit all review reports to the UMass Amherst IRB and NIMH Program Officer in annual progress reports.

The PI will be responsible for monitoring procedures during the study, including enrollment, data and sample collection, and participant safety and well-being. During the trial, experienced field supervisors from the Bhutanese community, who are trained as a community health worker and have worked with the PI in previous church and family-based mental health intervention studies with depressive and suicidal ideation outcomes, will take responsibility for the day-to-day oversight of the participants and field teams in the implementation of the trial. Field supervisors will immediately report any noted adverse events among participants, such as suicidal ideation, to the PI. The PI will report adverse events data to the ISM, UMass Amherst IRB, and NIMH Program Officer following NIMH guidelines for reportable events, as described below (<https://www.nimh.nih.gov/funding/clinical-research/nimh-reportable-events-policy.shtml>).

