needed. We plan to recruit two field supervisors from the Bhutanese community. Both are trained as community health workers and have extensive experience in providing various health services (including referral for mental health problems), as they are part-time employees of local level non-profit organizations (e.g., Ascentria Care Alliance) and the MA Department of Public Health. Both of them have worked with the PI in previous church and family-based mental health intervention studies with depressive and suicidal ideation outcomes. They are familiar with available mental health support services available in the community and have been providing care and support to the community members in a mental health crisis, bearing the dual responsibility of community leader and church pastor. Field supervisors will make regular follow-up visits to monitor participants' mental health conditions. A pamphlet will be provided to participants who need additional help, which describes the community's psychological services. We handled such cases successfully when we conducted our previous three studies, all of which included needs assessments, church-based and family-based mental health promotion interventions, measured suicidal ideation and depressive symptoms, and utilized our well-established networks in the clinical and community settings.

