9.2 Data Analyses

Baseline and follow-up data will be entered into an Excel database and exported to SAS statistical package for analyses. Privacy and security rules will be applied to protect the confidentiality and security of the data. Security features will be used at multiple levels, including the data element, user, application, and hosting services, with password protection for data access monitoring. These features will ensure control of access, authentication of users, and transmission security. The field team will be trained in project data maintenance.

Aim 2a Feasibility assessment: The PMP provides specific guidelines for evaluating and monitoring the intervention that we will use to monitor intervention delivery's fidelity. These tools are PMP Quiz, PMP Helper's Supervision Form, PMP Helper Classroom-based Competency Assessment, PMP Helper In-field based Competency Assessment, PM+ Trainer/Supervisor Competency Assessment, and Session-by-Session Checklists for PMP Helpers. Using these standard tools, we will evaluate session-by-session classroom and in-field based competencies of participants, community trainers, and supervisor and provide them feedback as needed using supervision forms, role-plays, group discussion, and training.

Community field supervisors will collect data on eligibility, recruitment and enrollment, intervention session attendance (including reasons for missed sessions), and compliance with data collection procedures, including hair sample collection and anthropometric measurements using a checklist. They will monitor intervention sessions using WHO standard checklists. Items include adherence to the manual, percent of intervention content administered, proper use of time/materials, and adequate response to participants' questions. They will also collect data on engagement, acceptability, and satisfaction via brief questionnaires and focus group discussions (FGD) with participants and interventionists after each session and upon intervention completion. The PI will conduct FGD in the Nepali language with interventionists, supervisors, and participants separately to collect information on barriers and facilitators of intervention, perceptions about whether the intervention met participants' needs, and feedback on how effectively the program team worked with participants. Interviews and FGD will be documented verbatim in a written transcript for subsequent analysis. All qualitative data will be analyzed using thematic

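### Field supervisors who oversee delivery also rate fidelity and collect satisfaction, so Aim 2a fidelity and acceptability scores are at risk of upward bias

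*Combined protocol and SAP*

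**What the plan says.** Section 9.2, Aim 2a, gives the field supervisors three kinds of feasibility data to collect.

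- Eligibility, recruitment, attendance and compliance, recorded on a checklist.
- Session fidelity: "They will monitor intervention sessions using WHO standard checklists". Section 5.2 gives them the same task by field observation: "The field supervisor will also collect data on adherence to the manual, percent of intervention content administered".
- Acceptability and satisfaction: "They will also collect data on engagement, acceptability, and satisfaction via brief questionnaires and focus group discussions (FGD) with participants and interventionists".

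The same people have a management role. Interventionists deliver under their supervision and the PI's (5.1). Section 7.2 adds that the supervisors "will take responsibility for the day-to-day oversight of the participants and field teams in the implementation of the trial". Section 7.3 plans for two of them and describes both as "bearing the dual responsibility of community leader and church pastor". They also help distressed participants to get appointments and make follow-up visits (4.1, 7.3).

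Two further statements bear on who rates. Section 5.1 trains the interventionists for a "dual role of interventionists and supervisors as needed". Aim 2a in Section 1.2 says that it will assess "the fidelity of intervention delivery, mediators of response, and outcomes using checklists from facilitators".

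**The concern.** A participant asked about satisfaction by a person of standing in a small community, who may also arrange their care, has a reason to answer kindly. So does an interventionist asked by the person who oversees their work. A supervisor scoring a session is partly scoring the team for which that supervisor is responsible. All three pressures push the scores up.

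This matters more here than in most trials because feasibility and acceptability are the declared objective, and the pilot is meant to inform a larger study (9.1, 9.2). If PMP-I shows little effect, the fidelity scores are what a reader would use to separate a programme that was poorly delivered from one that does not work. Lenient scores weaken that distinction.

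**Working it through.** No alpha, power, effect size or rate enters this point, and the plan states no fidelity or satisfaction threshold to reproduce. The check is to set out who collects each item and what stands behind it.

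| Aim 2a item | Collected by | Tie to delivery | Second source in the text |
|---|---|---|---|
| Session fidelity | Field supervisors (5.2, 9.2) | Supervise interventionists (5.1), oversee field teams (7.2) | PI site visits (7.2); PI review of fidelity forms (10.2.5) |
| Participant satisfaction and acceptability | Field supervisors (5.2, 9.2) | As above; community leaders and pastors (7.3) | PI focus groups (4.3, 5.2, 9.2) |
| Interventionist satisfaction | Field supervisors (5.2, 9.2) | Line of supervision | PI focus groups, held separately by role (5.2, 9.2) |
| Recruitment, attendance, retention | Field supervisors (5.2, 9.2) | As above | Counts, less open to leniency |

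**Volume of fidelity rating.** 58 PMP-I families (1.2) × 5 sessions (5.1) = 290 sessions. At 180 minutes each, 290 × 180 = 52,200 minutes = 870 hours. A fidelity form is scheduled at each session visit (6.1, 6.2.3). The PI's site visits are at least fortnightly, and one family's sessions run from Day 7 to Day 35, so about 28 ÷ 14 = 2 visits fall in that span, shared among all families then active. How many sessions would be seen cannot be calculated, because no session calendar is given.

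**Reach of the PI's focus groups.** Section 4.3 plans 30 participants from the intervention arm. If families average 2 to 4 adults (9.1), that arm holds 58 × 2 = 116 to 58 × 4 = 232 adults, so the groups reach between 30/232 = 13% and 30/116 = 26% of them. They must have attended the programme and are taken in order of coming forward (4.3), so non-attenders are left out.

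**Quality of the second sources.** The PI supervises delivery and gives the field training (5.1), and also analyses the data (10.1.6). The form review in 10.2.5 is for protocol deviations and looks at forms, not at sessions. The WHO-derived checklists (5.2) standardise the items but not the rater. The text describes no independent rater, recording, double rating or agreement check.

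**Mode of asking.** Section 2.1 describes the population as typically not literate, and 4.3 allows a fingerprint on the consent form. Satisfaction questions may therefore often be put aloud by the supervisor. This is an inference; the plan does not state the mode.

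**Who runs the participant focus groups.** Section 4.3 gives them to the PI. Sections 5.2 and 9.2 list focus groups with participants among the field supervisors' tasks and then say that the PI conducts them. The text does not settle which.

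**The case against.** The best defence is that the plan does not rely on supervisors alone. Directly after the sentence on questionnaires, 9.2 has the PI hold separate focus groups with interventionists, supervisors and participants on barriers, unmet needs and how well the team worked. Supervisors are themselves assessed for competency (5.2). Attendance, reasons for missed sessions and retention would show poor uptake whoever asks about satisfaction. Community-led monitoring is a deliberate choice in this pilot, and research assistants are local too. Most of this stands, and it limits the point to a risk with a partial check.

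A reader might also infer four stronger things that the documents do not support.

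- *That interventionists will rate their own or each other's sessions.* Section 5.1 describes the supervision they are trained for as discussion of progress and difficulties, and role-play. Fidelity rating is given to field supervisors, who are named separately. The Aim 2a reference to facilitators' checklists leaves the source unclear but does not establish self-rating.
- *That no rule prevents it.* The adapted monitoring tools are attached to the protocol (5.2) but were not available here, and may contain rater rules.
- *That supervisors are the participants' own pastors.* Section 7.3 gives their roles; it does not say that participants belong to their congregations.
- *That a decision to proceed rests on these scores.* No progression criterion is stated, and 9.1 and 9.2 tie the larger trial to effect-size estimates.

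**Conclusion.** The point holds as a risk. Fidelity and satisfaction are collected by people who oversee delivery and have standing in the community, and no independent rating is described. Upward bias is the likely direction, on the ordinary assumption that people answer and rate more favourably under such ties. Its size is unknown, and nothing in the documents allows an estimate.

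It would go too far to say that the results are biased, or that low acceptability could not appear: the attendance and retention counts and the PI's separate focus groups could both reveal it. The point is limited to the fidelity and acceptability scores and depends on the attached tools not already dealing with it.

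**What to change.** In Sections 5.2 and 9.2 (Aim 2a):

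1. Have a research assistant who did not attend that family's sessions put the acceptability and satisfaction items to PMP-I participants in the private individual interview, and make this the main acceptability result. The interview is already provided for (10.1.6) and Day 42 is already scheduled (6.1, 6.2.3). Ask these items after the primary outcome scales, so that they neither prime those answers nor reveal the arm beforehand. Keep the brief per-session forms as secondary. Section 4.3 does not follow people who end participation, whereas Section 8 asks them to continue, so a Day 42 measure alone could lose those who stop early.
2. State that nobody completes the fidelity form for a session they delivered, and report fidelity by rater role. If the attached tools already say this, refer to them.
3. Reconcile 4.3, 5.2 and 9.2 on who runs the participant focus groups.

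The cost is a slightly longer Day 42 interview and probably less favourable scores. No new staff are needed, since research assistants are listed apart from interventionists and supervisors (10.2.2). A research assistant who learns the arm at Day 42 may carry that knowledge to the final visit, but the trial declares no masking, so no stated blinding is lost. Some courtesy towards local research assistants will remain, and so will supervisor leniency in fidelity ratings; the latter should be reported as a limitation.
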